Examining the impact of acute blood flow restricted aerobic exercise on PGC-1 α mRNA expression in young healthy males: A randomized cross-over trial

NCT03717948

June 24, 2019

Statistical Analysis

Descriptive statistics will be used for baseline participant characteristics. Testing for carryover effects for the primary outcome will be conducted in accordance with the statistical procedures outlined by Wellek and Blettner (Wellek and Blettner 2012). To compare the effect of exercise on mRNA expression within each experimental session and also to compare group means for baseline mRNA expression and changes in mRNA expression between CTL and BFR, paired t-tests will be performed on linear data using the $2^{-\Delta Cq}$ (BL vs. +3 h) and $2^{-\Delta\Delta Cq}$ (CTL vs. BFR) methods (Schmittgen and Livak 2008) with TBP as a housekeeping gene. Average heart rate, lactate, RPM, and ratings of perceived exertion (RPE) during CTL and BFR will be compared using paired t-tests. Corresponding effect sizes for a within-subjects design (G*Power) will be interpreted as small ($d = 0.2$), medium ($d = 0.5$), and large ($d = 0.8$ (Cohen, 1988, pp 284-288). Protein content (+3 hours – PRE; +0 hours - PRE), NIRS, and EMG data from BFR and CTL will be analyzed using with a two-way repeated measures ANOVA (condition x time). Leg specific RPE will be also analyzed using a two-way repeated measures ANOVA (condition x biopsy status). Any significant interaction or main effects will be subsequently analyzed using Bonferroni *post-hoc* analyses. Corresponding effect sizes will be interpreted using partial eta (η) squared values (small = 0.0099; medium = 0.588; large = 0.1379) (Cohen, 1988, pp 284-288). All statistical analysis will be performed using SPSS Version 25 (IBM) and GraphPad Prism Version 8.0. Statistical significance will be set at $p < 0.05$, and all data will be presented as means \pm SD.

A priori sample size calculations were calculated for the primary outcome, between-group differences in fold change for PGC-1 α mRNA. Power calculations using G*Power revealed that a sample size of 12 was required to detect a statistically significant large effect size ($d = 0.9$, a conservative estimate based on the findings of Christiansen and colleagues (Christiansen et al. 2018)) between BFR and CTL with 80% power ($d = 0.9$, α err prob = 0.05, $1 - \beta$ prob = 0.8).

References

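### The primary BFR-versus-CTL comparison in this cross-over is a paired t-test with no period term, so a session-order shift in the exercise response would reduce power and, with unequal completers per sequence, bias the estimate.

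*SAP*

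**What the plan says.** The SAP's title calls the study "A randomized cross-over trial". The sample-size paragraph gives the primary outcome as "between-group differences in fold change for PGC-1 α mRNA". The first paragraph of Statistical Analysis names the test for that contrast: "changes in mRNA expression between CTL and BFR, paired t-tests will be performed on linear data".

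One step is specific to the cross-over design: "Testing for carryover effects for the primary outcome will be conducted in accordance with the statistical procedures" of a cited tutorial on cross-over trials. That citation is attached to the carryover test only. No period effect, sequence term, period-adjusted test or mixed model is specified for the BFR-versus-CTL comparison.

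The sample size is given in the second paragraph: a "sample size of 12 was required to detect a statistically significant large effect size", with d = 0.9, α = 0.05 and 80% power. Neither the sidedness of the test nor the number of participants per sequence is stated.

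**The concern.** Let τ be the true BFR minus CTL difference and π the amount by which the response in one session exceeds that in the other because of session order alone. The within-person difference then has mean τ + π in one sequence and τ − π in the other. A paired t-test pools the two sequences and treats the gap of 2π between them as noise. Two consequences follow.

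- With equal sequences the shift averages out of the estimate, but it inflates the standard error. The test becomes conservative and loses power.
- With unequal sequences the shift does not average out, and part of it enters the estimated treatment effect.

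The carryover test addresses a different question and leaves both consequences in place. Expressing expression relative to each session's own baseline largely cancels an order shift in baseline level. It does not cancel an order shift in the exercise response, for example if participants respond less to the second bout. Planned power is 80% with 12 participants, so there is little reserve.

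**Working it through.** **Inputs.** From the SAP: n = 12, d = 0.9, α = 0.05, power 80%, paired t-test. Assumed: two-sided test, two sequences, normally distributed differences, and d read as the mean difference divided by the SD of the differences. The shift π is in units of the within-sequence SD of the paired difference (set to 1). The SAP gives no value for π, so a range is shown.

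**Step 1: the plan's own figure.** Paired t-test, df = n − 1, noncentrality 0.9·√n. Power is 76.7% at n = 11 and 81.0% at n = 12, so n = 12 reproduces. A one-sided test would need only 10, which supports the two-sided reading.

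**Step 2: the period-adjusted test.** The estimate is the average of the two sequence-specific mean differences. Its SE is 0.5·√(1/n1 + 1/n2), with df = n − 2 = 10. Noncentral-t power at effect 0.9, whatever the shift:

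- 6:6: 80.2%
- 7:5: 79.1%
- 8:4: 75.5%

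**Step 3: paired test at 6:6 under a shift.** Simulation, at least 200,000 trials per cell, differences = τ ± π + N(0, 1).

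| π (SD) | Paired power, τ = 0.9 | Paired type I error, τ = 0 |
|---|---|---|
| 0 | 81.0% | 5.0% |
| 0.15 | 80.3% | about 4.8% |
| 0.25 | 79% | 4.4% |
| 0.5 | 73% | 3.0% |
| 0.75 | 63% | 1.6% |
| 1.0 | 50% | 0.6% |

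The adjusted test stays at 80.2% power and 5% type I error throughout, so the two tests break even near π = 0.15 SD.

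**Step 4: the other reading of d.** Suppose instead that 0.9 is relative to the SD of the observed differences, period spread included. Then τ = 0.9·√(1 + π²), which is 1.006 at π = 0.5 and 1.273 at π = 1.0. At 6:6:

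- π = 0.5: paired 83%, adjusted 88%
- π = 1.0: paired 87%, adjusted 98%

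Here the paired test does not fall below plan, but it still has less power than the adjusted test.

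**Step 5: unequal completers (assumed splits).** Bias of the paired estimate = π·(n1 − n2)/12, that is 2/12 = 1/6 of π at 7:5 and 4/12 = 1/3 of π at 8:4. At π = 0.5 SD:

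| Split | Bias (SD) | Paired power, shift favourable / unfavourable | Adjusted power |
|---|---|---|---|
| 7:5 | ±0.083 | 81% / 64% | 79.1% |
| 8:4 | ±0.167 | 88% / 55% | 75.5% |

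The paired test's type I error stays at or below about 5% at 7:5 and peaks near 5.6% at 8:4.

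**Step 6: mean squared error.** The unadjusted estimate has MSE 1/12 + bias²; the adjusted estimate has MSE (1/4)(1/n1 + 1/n2).

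- 7:5: 0.0833 + (π/6)² = 0.0857 gives π = 0.29 SD
- 8:4: 0.0833 + (π/3)² = 0.0938 gives π = 0.31 SD

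Below these shifts the unadjusted estimate is the more accurate of the two.

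**The case against.** The plan is internally consistent: a within-person contrast, a paired test, and a sample size built on that same test. At 6:6 the paired test is unbiased and never exceeds its nominal error rate, so the choice can be seen as one between two valid analyses. The SAP gives no reason to expect a period effect, and the larger shifts are extreme on its own scale: 1.0 SD exceeds the 0.9 SD effect the trial was sized for. At 0.25 SD only about 2 points of power are lost. The usual within-subject d divides by the SD of the observed differences, and on that reading planned power is kept. Bias needs both a material shift and unequal completers, and sequence numbers are commonly left to the protocol. At just those unequal splits, adjustment takes power below 80% when no shift exists.

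All of this is correct as fact, and it limits the weight of the point: false-positive risk is hardly affected, and small shifts do no harm. It does not remove the point. On either reading of d, the adjusted test has more power at 6:6 once the shift is appreciable. The paired test's advantage at unequal splits under a favourable shift comes partly from bias. In the unfavourable direction, at 0.5 SD, the adjusted test is clearly better (79% against 64% at 7:5, 76% against 55% at 8:4). Nor does the cited tutorial settle the matter, because the SAP invokes it for carryover alone and then names a different test for the treatment contrast.

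**Conclusion.** The point holds. The primary contrast makes no allowance for period, and the carryover test does not supply one. The consequence is conditional on a session-order shift in the exercise response, whose size the SAP does not give. At 6:6, with d relative to the within-sequence SD, the loss against the unshifted 81% is about 2 points at 0.25 SD, 8 at 0.5 SD and 31 at 1.0 SD, with no inflation of type I error. If d already includes period spread, the cost is power forgone (5 points at 0.5 SD, 11 at 1.0 SD) and not a shortfall against plan. With unequal completers there is also a bias of 1/6 (7:5) or 1/3 (8:4) of the shift. All figures assume normal differences and a two-sided 5% test. This should be changed, but it does not invalidate the trial.

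**What to change.** Replace the paired t-test for the primary outcome with a prespecified period-adjusted cross-over test. This can be a two-sample t-test of the period differences (first session minus second) between the two randomised sequences (Hills-Armitage). It can equally be a mixed model with condition, period and sequence as fixed effects and participant as random. Name one of the two in the SAP. Report the adjusted BFR minus CTL difference with its 95% confidence interval and the number of completers in each sequence. The same model may be used for the secondary paired comparisons, but this is optional.

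The change should be fixed before the data are seen; deciding on adjustment afterwards would weaken the primary result. It costs one sentence and one degree of freedom (11 to 10), with no new data and no more participants. If there is no period effect, power goes from 81.0% to 80.2% at 6:6. At 7:5 it would be 79.1% and at 8:4 75.5%, both below the planned 80%, and that price should be accepted knowingly.

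### Post-hoc tests on protein, NIRS, EMG and leg RPE: Holm on the BFR–CTL contrasts would reject at least as much as plain Bonferroni at the same family-wise error (optional improvement, not an error)

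*SAP*

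**What the plan says.** The first paragraph of the SAP's Statistical Analysis section assigns a two-factor repeated-measures ANOVA to protein content (two change scores, immediately and three hours after exercise, each against the pre-exercise value), to NIRS and to EMG. The factors are condition and time. For leg RPE it adds: "Leg specific RPE will be also analyzed using a two-way repeated measures ANOVA (condition x biopsy status").

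One sentence governs the follow-up of all four: "Any significant interaction or main effects will be subsequently analyzed using Bonferroni" post-hoc analyses. It names no step-down version and does not list the contrasts that are corrected together. The number of NIRS and EMG time points is not given.

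The primary outcome takes another route. For mRNA, "paired t-tests will be performed on linear data", with no Bonferroni step. The second paragraph sizes the trial on that outcome alone: "A priori sample size calculations were calculated for the primary outcome", and "a sample size of 12 was required to detect a statistically significant large effect size" (0.9, with 80% power and alpha 0.05).

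**The concern.** Single-step Bonferroni tests every contrast at 0.05/m. Holm tests the smallest p-value at 0.05/m, the next at 0.05/(m − 1), and so on, stopping at the first failure. It therefore rejects everything that Bonferroni rejects, sometimes more, and bounds the family-wise error at the same 0.05 under any dependence between contrasts. With 12 participants, the plan gives up some power on its non-primary outcomes for no gain in error control.

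What is at stake is limited: some real BFR–CTL differences in protein, NIRS, EMG or leg RPE may go undeclared when several are present together. The primary conclusion does not depend on it.

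**Working it through.** **Inputs.** From the SAP: n = 12, alpha 0.05, d = 0.9. My assumptions: two-sided tests; d = 0.9 carried over from the primary outcome to every real contrast; paired contrasts on 11 df; equal correlation between contrasts. Two contrasts apply to protein (two change scores) and to leg RPE (read as 2 × 2). Three to six contrasts are an assumed range for NIRS and EMG.

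**1. The SAP's own figure.** For a paired t-test, power = P(|T| > t critical), with T noncentral t on n − 1 df and noncentrality d√n. At n = 11 power is 76.7%. At n = 12 (noncentrality 0.9 × √12 = 3.118) it is 81.0%. So N = 12 reproduces with a two-sided test; a one-sided test would need only 10.

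**2. Bonferroni at n = 12.** The same formula at 0.05/m gives, per contrast: m = 1, 81.0%; m = 2, 69.7%; m = 3, 62.4%; m = 4, 57.1%; m = 5, 53.0%; m = 6, 49.7%.

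**3. Holm with two real, independent contrasts.** Let A = 0.8098 (power at 0.05) and B = 0.6965 (power at 0.025).

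- Per contrast: B + (A − B) × B = 0.6965 + 0.1133 × 0.6965 = 0.775, against 0.697 for Bonferroni.
- Both contrasts: A² − (A − B)² = 0.6558 − 0.0128 = 0.643, against B² = 0.485.
- At least one: 1 − (1 − B)² = 0.908 for both methods.

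**4. Correlation 0.5, all contrasts real, by simulation (at least 100,000 sets).**

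| Contrasts | Per contrast, Bonferroni | Per contrast, Holm | All found, Bonferroni | All found, Holm |
|---|---|---|---|---|
| 2 | 69.6% | 76.5% | 54.3% | 68.1% |
| 3 | 62.4% | 72.4% | 35.9% | 58.5% |
| 4 | 57.1% | 68.9% | 24.0% | 51.1% |
| 5 | 52.9% | 65.8% | 16.2% | 45.3% |
| 6 | 49.4% | 62.7% | 11.2% | 40.5% |

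At correlation 0, five contrasts go from 53.0% to about 67% per contrast.

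**5. When fewer contrasts are real.** With one real and one null contrast, independent, Holm adds (A − B) × 0.025 = 0.1133 × 0.025 = 0.0028, about 0.3 points. Over the settings simulated, the gain for a single real contrast is 0 to 0.3 points. With two real contrasts out of four (correlation 0.5), power per real contrast goes from 57.1% to 60.1%.

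**6. Error control.** With two null contrasts (correlation 0.5), family-wise error is the same for both methods, about 4.6%. With one null and one real it is 2.4% for Bonferroni and 4.1% for Holm. Both stay below 5%.

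**7. Size of the family.** A 2 × 2 layout has 4 × 3/2 = 6 cell pairs, of which 2 compare BFR with CTL in the same leg or at the same time. If all 6 were corrected together, power would be 49.7%; over the 2 it is 69.7%. This gain is separate from Holm and arises only if the wider family was intended.

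**8. The trigger.** I modelled the SAP's trigger as a significant interaction or a significant condition effect, with two time points. With 0.9 at both, Bonferroni gives about 69–70% per contrast and Holm 76–77%, so the trigger costs almost nothing. If the contrasts were run only after a significant interaction, power would fall to about 3.5%, because equal effects produce no interaction and that test is significant in only 5% of trials.

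**The case against.** The strongest reply is that nothing here is wrong. Bonferroni after an ANOVA is valid and conservative, the outcomes are not primary, and the SAP states no effect size or power target for them. All of that stands, and it is why the point is optional.

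The case against also limits the size of the gain. Holm helps when two or more contrasts are real. A crossed pattern with an effect at one time only, which is where an interaction is most likely, gains next to nothing. Nor does Holm improve the chance of finding at least one effect when all are real. This stands too.

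Several stronger readings are tempting, and the SAP does not support them:

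- **That alpha is spread over 6 pairs in a 2 × 2 layout, or 45 with five time points.** The SAP names no family, and the same-time or same-leg contrasts may be exactly what is meant. The power actually lost cannot be computed from the document.
- **That power is lost after every main effect.** Condition has two levels, and biopsy status presumably does too. Each main effect is then one contrast with no correction. A time main effect calls for comparisons between times, not BFR against CTL.
- **That main effects will be misread when the interaction is significant.** The trigger permits main-effect follow-up in that case, but the SAP does not say that an average over conditions will be interpreted as holding in each.
- **That BFR–CTL contrasts should wait for a significant interaction.** With 0.9 at one time and 0 at the other, that gate gives 46% (correlation 0) and about 61% (correlation 0.5) for the real contrast. Bonferroni over two contrasts under the SAP's trigger gives 65% and 68%. With equal effects the gate removes nearly all per-time power.

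**Conclusion.** The point holds as a cheap efficiency gain for protein, NIRS, EMG and leg-specific RPE. It is not an error in the plan. On the same contrasts, Holm never does worse than Bonferroni on rejections and keeps family-wise error at or below 0.05.

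If both of two contrasts are real at d = 0.9, power per contrast goes from 70% to 76–78% and power for both from 49–54% to 64–68% (correlation 0.5 to 0). The benefit grows with the number of real contrasts and almost vanishes when only one is real. These figures rest on an effect size borrowed from PGC-1α mRNA and, beyond two contrasts, on assumed numbers of time points. They are illustrations and not estimates of this trial's power.

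A reader might infer that the trial is underpowered or its main result weakened. It is not: N = 12 reproduces at 81.0% power for the primary paired t-test, which carries no Bonferroni correction.

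**What to change.** Keep the SAP's trigger and replace the post-hoc sentence with wording such as:

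> *If the interaction or a main effect is significant, BFR will be compared with CTL at each time point (for leg-specific RPE, within each leg) by paired contrasts, Holm-adjusted over those contrasts. A significant main effect of time with more than two levels will also be followed by pairwise comparisons between time points, Holm-adjusted over those comparisons.*

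This settles which contrasts form each family and leaves the BFR–CTL contrasts free of any requirement for a significant interaction. Holm controls the error over its contrasts by itself, so it does not need such a gate.

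The change costs SAP wording only. Holm needs just the ordered unadjusted p-values, and no data collection or sample size is affected. There are two losses. Holm has no simple matching simultaneous confidence intervals, so intervals would have to be reported unadjusted or with Bonferroni width and labelled accordingly. Comparisons of BFR at one time with CTL at another (or across legs) would no longer be tested.
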